1.1 Background

Urticaria, also known as hives, is a common dermatologic condition which presents with the rapid appearance of pale to brightly colored wheals of various sizes ranging from several millimeters to several centimeters, with or without surrounding erythema, pruritus or occasional burning sensations, and the skin returning to normal typically within one to twenty-four hours (1) (2). The pathophysiologic mechanism involves the release of histamine and other mediators from mast cells and basophils; release in the dermis results in urticaria while release in the deeper dermis and subcutaneous tissues results in angioedema (2). Most commonly, symptoms are caused by exposure to allergens, foods, insect venom, medications, and viral infections. Persons of any ages may present with urticaria, with a lifetime prevalence of between 15% and 25% (2) (3)(4).

Acute urticaria is defined as urticaria persisting less than 6 weeks, whereas chronic urticaria persists 6 weeks or longer (2)(5)(6). Second-generation H1 antihistamines are first-line medication for the treatment of acute urticaria. In some cases, they may be titrated to two or even four times the normal dose to control symptoms followed by H2 antihistamines and corticosteroid for severe cases (1)(2). Indication for epinephrine includes emergency treatment of type 1 hypersensitivity reactions (7) and epinephrine injection is recommended in medical prescribing guidelines in the United States (US) for the management of acute flares with associated angioedema in patients with urticaria. Acute urticaria is treated with but often unresponsive to antihistamines and corticosteroids. Intramuscular (IM) epinephrine is typically efficacious in alleviating urticarial flares.

Epinephrine, illustrated in Figure 1 below, is a sympathomimetic catecholamine. Chemically, epinephrine is B-(3, 4dihydroxyphenyl)-a-methyl-aminoethanol. Epinephrine solution deteriorates rapidly on exposure to air or light, turning pink from oxidation to adrenochrome and brown from the formation of melanin. It is a colorless to light yellow crystalline compound, insoluble in water. The formula is $C_9H_{13}NO_3$ and the molecular weight is 183.20442.

Figure 1: Epinephrine

ARS Pharmaceuticals, Inc. (ARS) is investigating an epinephrine nasal spray (ARS-1) for patients with urticaria as a needleless alternative route of epinephrine administration for the treatment of urticarial flares.

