- Acute flare: at least 2 hours after dosing and can discharge when the discharge criteria is met (the time when symptoms of acute urticaria have been effectively treated based on the investigator's or his/her designee's opinion will be recorded, not necessarily when

subjects discharged). If no relief of pruritus symptoms after 2 hours, other acute interventions may be administered as rescue.

- Chronic spontaneous urticaria: until the urticaria symptoms returns to the baseline.

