3.3 Efficacy Assessments

The following efficacy assessments will be evaluated based on self-reported and clinical assessments of pruritus at pre-dose, and at 5 (± 2 min), 10 (± 2 min), 15 (± 3 min), 30 (± 5 min), 45 (± 5 min), 60 (± 10 min), 120 (± 10 min) minutes, and every 60 minutes (± 10 min) after dosing until the discharge criteria (the time when symptoms of acute urticaria have been effectively treated based on the investigator's or his/her designee's opinion will be recorded, not necessarily when subjects discharged) is met for acute flare and until urticaria symptoms returns to the baseline for chronic spontaneous urticaria. If the time to return to baseline for chronic spontaneous urticaria is beyond 4 hours, such time may be recorded by the patient and reported in the follow-up call. The actual time of the assessment and of when the symptoms return to the baseline will be recorded. Subjects should also record the date and time of recurrence, if any, of symptoms after they leave the clinic.

- A patient reported pruritus/hive score from 0 (none) to 3 (severe) for itch and hive using Uniform Assessment System (UAS) twice daily as below:

| Itch Severity Score | Amount of Itch | Itch Severity at Each Assessment |
|---------------------|----------------|--|
| 0 | None | None |
| 1 | Mild | Minimal awareness, easily tolerated |
| 2 | Moderate | Definite awareness, bothersome but tolerable |
| 3 | Intense | Difficult to tolerate |

| Hive Severity Score | Number of Hives at Each Assessment |
|---------------------|------------------------------------|
| 0 | None |
| 1 | 1-6 |
| 2 | 7-12 |
| 3 | >12 |

- Patient reported pain associated with the urticaria flare will be recorded based on a self-reported VAS score

- An investigator-rated extent of urticaria; % of body area with urticaria (Grade 1: urticarial lesions covering < 10% body surface area [BSA]; Grade 2: urticarial lesions covering 10-30% BSA; Grade 3: urticarial lesions covering > 30% BSA)
- An investigator-rated erythema score (0 = none, 1 = almost clear [slight redness], 2 = mild erythema [definite redness], 3 = moderate erythema [marked redness], 4 = severe erythema [fiery redness])

[REDACTED]

[REDACTED]

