10.5 Discharge Assessments (Treatment Periods 1 - 3)

Discharge assessments will be completed by the Investigator or his/her designee once symptoms of urticaria have been effectively treated for an acute flare or returned to baseline for chronic spontaneous urticaria. Actual time by hours and minutes will be recorded. In addition, AEs and concomitant medication will also be recorded.

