14.3 Efficacy Data Analyses

14.3.1 Primary Efficacy Analyses

The baseline for the primary endpoints will be the pre-dose at each visit.

Superiority comparison of ARS-1 1 mg vs. placebo and ARS-1 2 mg vs. placebo at each timepoint will be tested at the two-sided 0.05 significance level. If both ARS-1 1 and 2 mg are statistically superior to placebo, comparison between the ARS-1 doses will be conducted.

Time to effect is defined to be the time that it takes to lower one grade, two grades, and three grades.

Duration of effect is defined as the time from when the grade becomes above baseline until the grade returned to baseline.

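### Duration of effect as defined in section 14.3.1 times worsening, and even with its start corrected it gives no value to a flare that clears and stays clear

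*Combined protocol and SAP*

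**What the plan says.** Section 2.1 places time to effect and duration of effect, based on the patient-reported pruritus/hive score, under the primary objectives. Section 14.3.1 then gives three linked statements:

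- Baseline: "The baseline for the primary endpoints will be the pre-dose at each visit".
- Time to effect: "Time to effect is defined to be the time that it takes to lower one grade, two grades, and three grades".
- Duration: "Duration of effect is defined as the time from when the grade becomes above baseline until the grade returned to baseline".

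Section 3.3 defines the scale: "A patient reported pruritus/hive score from 0 (none) to 3 (severe) for itch and hive". A higher score is worse.

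The word baseline also governs data collection. Section 3.1 sets the clinic stay: "Chronic spontaneous urticaria: until the urticaria symptoms returns to the baseline". Section 3.3 ends the scheduled scoring for this group in the same way. It adds that if the return "is beyond 4 hours, such time may be recorded by the patient and reported in the follow-up call". It also asks all subjects to record any recurrence after they leave the clinic. Section 10.5 has the discharge assessment done once symptoms have been effectively treated (acute flare) or "returned to baseline for chronic spontaneous urticaria".

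The synopsis (Statistical Analysis) assigns all quantitative endpoints to linear mixed models. No visible text names a censoring rule, a time-to-event method or a category for flares that do not return.

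**The concern.** The definition fails at both ends.

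**Start.** Benefit is a lower grade, as the time-to-effect definition confirms. A clock that starts when the grade rises above its pre-dose value therefore measures a spell of worsening.

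**End.** Suppose the start is read as a fall below baseline, which is presumably what was meant. The clock then stops only when the pre-dose grade is reached again. A flare that resolves for good never gets there. This should not be rare, because section 1.1 describes urticaria with "the skin returning to normal typically within one to twenty-four hours".

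The periods left without a value are the best outcomes. If they drop out of the analysis, the durations that remain come from periods in which the effect wore off, and more periods are lost under the longer-acting treatment. The comparison of 1 mg, 2 mg and placebo on a primary-objective measure would then be attenuated, or would depend on a handling rule chosen after the data are seen.

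**Working it through.** The plan states no figure for this measure, so there is none to reproduce. Two checks follow.

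**1. The definition applied to worked profiles** (scheduled times 5, 10, 15, 30, 45, 60, 120, 180 and 240 minutes; invented grades)

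| Profile | Literal start (above pre-dose) | Start read as below pre-dose |
|---|---|---|
| 3 pre-dose, 2 at 10 min, 0 from 30 min onward | no duration | starts at 10 min, never ends |
| 3 pre-dose, 2 at 10 min, back to 3 at 120 min | no duration | 120 − 10 = 110 min |
| 2 pre-dose, 3 at 10 min, back to 2 at 45 min | 45 − 10 = 35 min of effect | no duration |
| 3 throughout | no duration | no duration |

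Read literally, the only profile that earns a duration is the one that got worse. With the start corrected, the complete response still has none.

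**2. Size of the attenuation if undefined periods are dropped** (all inputs assumed)

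Let W be the time until the effect wears off, exponential with mean m = 2 h or 8 h (true ratio 4). Let E be the natural end of the flare, independent of W. Onset is taken as immediate. A duration is observed only if W < E.

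- Share with no duration: q = E[exp(−E/m)].
- Mean of the observed durations: m − E[E·exp(−E/m)] / (1 − q).

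*Setting A:* E = 1 h plus an exponential of mean 4 h (the 24 h cap changes little and is left out of the formulas).

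- q = exp(−1/m) × m/(m + 4).
- m = 2: 0.6065 × 2/6 = 0.202. m = 8: 0.8825 × 8/12 = 0.588.
- E[E·exp(−E/m)] = exp(−1/m) × [m/(m + 4) + 0.25/(0.25 + 1/m)²].
- m = 2: 0.6065 × (0.3333 + 0.4444) = 0.472, so the mean is 2 − 0.472/0.798 = 1.41 h.
- m = 8: 0.8825 × (0.6667 + 1.7778) = 2.157, so the mean is 8 − 2.157/0.412 = 2.76 h.

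*Setting B:* E uniform over the 1 to 24 h of section 1.1.

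- q = (m/23) × [exp(−1/m) − exp(−24/m)].
- m = 2: (2/23) × 0.6065 = 0.053. m = 8: (8/23) × (0.8825 − 0.0498) = 0.290.
- E[E·exp(−E/m)] = (m/23) × [(1 + m)·exp(−1/m) − (24 + m)·exp(−24/m)].
- m = 2: 0.158, so the mean is 2 − 0.158/0.947 = 1.83 h.
- m = 8: 2.208, so the mean is 8 − 2.208/0.710 = 4.89 h.

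| | No duration, m = 2 / m = 8 | Observed means | Apparent ratio (true 4) |
|---|---|---|---|
| A | 20% / 59% | 1.41 h / 2.76 h | 2.0 |
| B | 5% / 29% | 1.83 h / 4.89 h | 2.7 |

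If the unreturned periods are instead right-censored at E, total observed time divided by the number of returns gives 2.0 h and 8.0 h in both settings (in A, 1.596/0.798 and 3.293/0.412). Censoring removes the attenuation here.

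A different model gives an extreme case. Let relapsers return with a median of 1 h in both arms, let 50% versus 10% stay clear, and observe for 4 h. Dropping undefined periods gives a difference of 0.00 h. The true difference in mean duration restricted to 24 h is about 9.0 h.

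**3. A 0 to 120 minute measure under the same inputs.** Minutes at least one grade below pre-dose, with a cleared flare credited to 120 minutes, average about 1.27 h versus 1.77 h in both settings, a ratio of about 1.4. About 78% to 79% of the long-acting periods sit at the ceiling. The measure scores every fully assessed period but compresses the ratio more than dropping does.

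**The case against.** The strongest reply has four parts.

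**The stop rule may use another baseline.** A reader might infer that a cleared chronic spontaneous flare can never meet its assessment or discharge rule. The documents do not support that as a flat statement. Section 14.3.1 defines baseline only for the primary endpoints, and section 10.5 sets return to baseline beside effective treatment, so it may mean the usual state between flares. On that reading the cleared flare does meet the rule. What stands is that the word then has two meanings.

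**The bias is not established.** A reader might infer that longer-acting treatment must look shorter. That follows only if undefined durations are dropped, or cut off at the last observation without being treated as censored. No visible text says so, and section 14.5 is redacted and might hold a rule. The single named method makes the bias plausible rather than certain.

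**Other data are collected.** A reader might take the 4-hour provision as the only capture of late events. It is not, because sections 3.3 and 6.0 also ask for any recurrence after leaving the clinic. Those records help to fix a censoring time, but they give no duration to a flare that never recurs.

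**The stakes are modest.** The synopsis calls all analyses exploratory, the objective names acute flares, and the wear-off times above are invented. This limits the severity. It does not rescue the definition, and the gap covers acute flares too: they are discharged once effectively treated, so a later return is seen only through self-report.

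**Conclusion.** The concern holds in a bounded form. As written, duration of effect times worsening. With the start corrected, a flare that clears and stays clear, in either urticaria group, has no end and no visible rule for a value. These two conclusions rest on the text alone, subject to the redaction of section 14.5.

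Attenuation of treatment differences is conditional on undefined periods being dropped. Its illustrated size, a true ratio of 4 shown as about 2.0 to 2.7, rests on assumed exponential wear-off, an assumed distribution of flare ends, independence of the two and immediate onset.

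Both meanings of baseline cause trouble. Under the pre-dose meaning, a cleared chronic spontaneous flare does not meet the assessment stop rule. Under the non-flare meaning, duration would end at clearance, and faster relief would score as a shorter effect. For an exploratory trial this should be corrected before analysis, because it leaves a primary-objective measure undefined for its best outcome.

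**What to change.** In section 14.3.1, for both urticaria groups:

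1. Define duration as the time from the first fall of at least one grade below the pre-dose score until the score is back at the pre-dose level.
2. Right-censor periods with no return at the last assessment or contact, using the return and recurrence times already collected. Because discharge depends on response, use later contact information where it exists rather than stopping every record at discharge.
3. Name a method that handles censoring and respects the crossover pairing, in place of the linear mixed model for this measure. If half or more of the periods stay clear, report the median as not reached.
4. Give periods with no fall a duration of 0, and report cleared with no return as its own category.
5. Optionally add minutes at least one grade below pre-dose over 0 to 120 minutes as a supportive measure, stating its ceiling.
6. State one meaning of baseline for analysis, and reconcile the uses in sections 3.1, 3.3, 10.3 and 10.5 with it.

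The cost is protocol and SAP wording, with no new assessments. The remaining weakness is that late return times are self-reported and, for chronic spontaneous urticaria beyond 4 hours, optional, so some censoring times will be imprecise.

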14.4 Safety Data Analyses

Safety variables to be monitored include AEs and vital signs. Safety data will be collected throughout the study and summarized using descriptive statistics.

The incidence and severity of AEs reported during the study and their relationship to study drug will be tabulated. AEs will be coded using MedDRA™ and will be presented by body system. The incidence of laboratory abnormalities as determined by CTCAE v 5.0 will be summarized for each dose cohort and time point.

The World Health Organization Drug Dictionary (WHODD) will be used to classify prior and concomitant medications by therapeutic class and preferred term. Prior and concomitant medication usage will be summarized by the number and percentage of subjects receiving each medication within each therapeutic class by dose cohort.

14.5 [REDACTED]

[REDACTED]

[REDACTED]

[REDACTED]

[REDACTED]

[REDACTED]

[REDACTED]

[REDACTED]

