| Efficacy Assessments | 
The following efficacy assessments will be evaluated based on self-reported and clinical assessments of pruritus at pre-dose, and at 5 (± 2 min), 10 (± 2 min), 15 (± 3 min), 30 (± 5 min), 45 (± 5 min), 60 (± 10 min), 120 (± 10 min) minutes and every 60 minutes (± 10 min) after dosing until the discharge criteria (the time when symptoms of acute urticaria have been effectively treated based on the investigator's or his/her designee's opinion will be recorded, not necessarily when subjects discharged) is met for acute flare and until urticaria symptoms returns to the baseline for chronic spontaneous urticaria. [REDACTED]
 
[REDACTED] The actual time of the assessment and of when the symptoms return to the baseline will be recorded. Subjects should also record the date and time of recurrence, if any, of symptoms after they leave the clinic.
 
 A patient reported pruritus/hive score from 0 (none) to 3 (severe) for itch and hive using Uniform Assessment System (UAS) twice daily Patient reported pain associated with the urticaria flare will be recorded based on a self-reported VAS score An investigator-rated extent of urticaria; % of body area with urticaria (Grade 1: urticarial lesions covering < 10% body surface area [BSA]; Grade 2: urticarial lesions covering 10-30% BSA; Grade 3: urticarial lesions covering > 30% BSA) An investigator-rated erythema score (0 = none, 1 = almost clear [slight redness], 2 = mild erythema [definite redness], 3 = Moderate erythema (marked redness), 4 = |

| | |
|-----------------------------|---|
| | 
severe erythema [fiery redness])
 
[REDACTED]
 
[REDACTED]
 
[REDACTED]
 
[REDACTED]
 
[REDACTED]
 |
| Safety Analysis | 
AEs will be collected and reviewed to evaluate the safety and tolerability of ARS-1. AE collection will begin after dosing and continue until discharge. AEs may be either spontaneously reported or elicited during questioning and examination of a subject. AE information will be elicited at appropriate intervals by indirect questioning using a non-leading question.
 
Vital signs measurement (BP, pulse rate [PR], respiratory rate, and temperature will be taken at pre-dose, and at 5 (\pm 2 min), 20 (\pm 2 min), 30 (\pm 2 min), 60 (\pm 5 min) and 120 (\pm 5 min) minutes after dosing.
 
Actual reading times at the measurement by hour/minutes/seconds will be recorded.
 |

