9.0 SAFETY ASSESSMENTS

9.1 Collection of Adverse Events Data

Data regarding TEAEs will be collected in this study. TEAEs are events that are not present at baseline, or if present at baseline, have worsened in severity. AEs will be assessed while the subjects are in the study. AEs assessed by the Investigator as related to study drug and “ongoing” at discharge will be monitored by the Investigator until resolved or until the subject is deemed “lost to follow-up”.

Any AEs reported by the subject or noted by the Investigator or his/her designee will be recorded on the eCRF regardless of the Investigator opinion of causality. The following information will be recorded for each AE: description of the event, date and time of onset, date and time of resolution, severity, causal relationship to study drug, outcome, action taken with the study drug and any treatment given.

All abnormal changes from baseline will be collected, graded with regards to severity or clinical significance, assessed for causal relationship and recorded on the eCRF.

Refer to [Section 13.0](#) for further details.

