10.3 Drug Administration

After baseline safety assessments, subjects will be randomized to receive the following treatments at each of the three Treatment Periods:

- 1 mg per 100 μ L dose of ARS-1,
- 2 mg per 100 μ L dose of ARS-1, or
- placebo (100 μ L)

ARS-1 or placebo will be dosed to the nostril by the medical professional in a clinical setting per IFU ([Appendix B](#)). [REDACTED]

[REDACTED] Subjects will be monitored for both safety and symptom relief. Safety assessments will be performed after dosing and will include AEs and vital signs. Concomitant medications will be recorded.

Subjects should remain in the clinic as below:

- Acute flare: at least 2 hours after dosing and can discharge when the discharge criteria is met (the time when symptoms of acute urticaria have been effectively treated based on the investigator's or his/her designee's opinion will be recorded, not necessarily when subjects discharged). If no relief of pruritus symptoms after 2 hours, other acute interventions may be administered as rescue.

- Chronic spontaneous urticaria: until the urticaria symptoms returns to the baseline. [REDACTED]

The calendar date and 24-hour clock time of all doses will be recorded on the eCRF.

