13.0 SAFETY MONITORING AND ADVERSE EVENTS

13.1 Adverse Events

Data regarding TEAEs will be collected in this study. TEAEs are events that are not present at baseline, or if present at baseline, have worsened in severity.

Definition of Adverse Events and Adverse Drug Reactions:

AEs in the eCRF will be classified according to the most recent FDA definitions and in a manner consistent with International Conference on Harmonization (ICH) guidelines. As such the following definitions will be used:

An AE is any unfavorable and unintended sign, symptom, or disease temporally associated with the use of an investigational (medicinal) product (IP) or other protocol-imposed intervention, regardless of attribution. An AE may include intercurrent illnesses or injuries that represent an exacerbation (increase in frequency, severity, or specificity) of pre-existing conditions (e.g., worsening of asthma). A laboratory abnormality will be reported on the “Adverse Event” case report forms only if it is associated with clinical sequelae or requires therapeutic intervention.

Whenever possible, it is preferable to record a diagnosis as the AE term rather than a series of symptoms relating to a diagnosis. AEs will be coded according to the Medical Dictionary for Regulatory Activities (MedDRA) and graded according to the Common Terminology Criteria for Adverse Events (CTCAE) v 5.0 ([Appendix C](#)).

The reporting period for AEs starts after dosing and continues until discharge.

If an AE remains unresolved at discharge, the subject will be followed, at the Investigator’s discretion, until resolution of the event or until the subject is deemed “lost to follow-up”. AEs assessed by the Investigator as related to study drug and “ongoing” at discharge will be monitored by the Investigator until resolved or until the subject is deemed “lost to follow-up”. SAEs must be followed until resolution by the PI, even if this extends beyond the study-reporting

period. Resolution is defined as the return to baseline status or stabilization of the condition with the expectation that it will remain chronic.

The Investigator will assess AEs for severity, relationship to IP, and as to whether the event meets one or more of the definitions of an SAE. The assessments will be recorded on the source documents and AE case report form (CRF), using the categories defined below.

| Causality Category | Description |
|---------------------------|--|

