Appendix A: Schedule of Study Procedures

Table 1: Schedule of Study Procedures

| Study Procedure Study Day | Screening Day -90 to -1 | Treatment Period 1 | | Treatment Period 2 | | Treatment Period 3 | |
|--|----------------------------|-----------------------|-----------|-----------------------|-----------|-----------------------|-----------|
| | | pre-dose | post-dose | pre-dose | post-dose | pre-dose | post-dose |
| Signed informed consent | X | | | | | | |
| Inclusion/Exclusion Criteria | X | X | | | | | |
| Admission to Clinical Site | | X | | X | | X | |
| Medical history | X | X | | | | | |
| Complete or targeted physical exam | X | X | | X | | X | |
| Vital signs ^a | X | X | X | X | X | X | X |
| Height and Weight | X | | | | | | |
| Hematology, Serum Chemistry, Coagulation, and Urinalysis | X | | | | | | |
| HIV Antibody and Hepatitis Tests | X | | | | | | |
| Urine Drug and Cotinine, Saliva/Urine Alcohol Screen | X | | | | | | |
| Prior and Concomitant medication assessment | X | X | X | X | X | X | X |
| Urine pregnancy test ^b | X | | | | | | |
| Adverse event assessment ^c | | | X | X | X | X | X |
| ECG (12-Lead in triplicate) ^d | X | | | | | | |
| Study Medication | | | X | | X | | X |
| Patient reported pruritus/hive score and VAS for pain ^e | | X | X | X | X | X | X |
| Investigator-rated extent of urticaria and erythema score ^f | | X | X | X | X | X | X |
| | | | | | | | |
| | | | | | | | |
| | | | | | | | |
| Discharge assessment ^d | | | X | | X | | X |
| | | | | | | | |

- Vital signs (BP, PR, temperature, and respiratory rate) will be taken at pre-dose, and at 5 (\pm 2 min), 20 (\pm 2 min), 30 (\pm 2 min), 60 (\pm 5 min), and 120 (\pm 5 min) minutes after dosing. Actual times by hour/minutes/seconds will be recorded.
- A urine pregnancy test will be administered to females of childbearing potential at screening.
- AE assessment will begin after dosing and continue until discharge. AEs will also be solicited at the follow up telephone call.
- ECG is to be performed in triplicate.

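### AE incidence is tabulated by treatment with no common observation window and no split at rescue, so ARS-1 and placebo figures can cover unequal in-clinic time

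*Combined protocol and SAP*

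**What the plan says.** **Analysis.** Section 14.4 states "The incidence and severity of AEs reported during the study and their relationship to study drug will be tabulated" and "Safety data will be collected throughout the study and summarized using descriptive statistics". It gives no onset window, no time at risk and no separation at rescue. The safety set in Section 14.2 assigns each period's data to the treatment received in that period.

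**End of AE collection.** Section 13.1: "The reporting period for AEs starts after dosing and continues until discharge". The Synopsis agrees: "AE collection will begin after dosing and continue until discharge". The Appendix A footnote goes further: "AE assessment will begin after dosing and continue until discharge. AEs will also be solicited at the follow up telephone call". Section 9.1 has AEs assessed for as long as the subject is in the study.

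**Discharge.** Section 10.5 places the discharge assessment "once symptoms of urticaria have been effectively treated for an acute flare or returned to baseline for chronic spontaneous urticaria". Section 3.6 sets a 2-hour minimum stay. No common end point follows it.

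**Rescue.** Section 10.3, on acute flares: "If no relief of pruritus symptoms after 2 hours, other acute interventions may be administered as rescue". Section 3.1 asks only that rescue be avoided, where possible, in the first 15 minutes.

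**Data available.** Section 9.1: "The following information will be recorded for each AE: description of the event, date and time of onset". Appendix A has rescue use recorded at the discharge assessment.

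**The concern.** A table of plain incidences compares treatments fairly only if each treatment was watched for AEs over the same time. Here the intensive part of that observation ends at discharge, and discharge depends on symptoms.

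In an acute flare, a subject who responds can leave at 2 hours, while one who does not may be rescued and stay longer. In chronic spontaneous urticaria the stay lasts until symptoms are back at baseline. If baseline there means the pre-dose state, a responder stays until the effect wears off and a non-responder has nothing to wait for beyond the 2-hour minimum.

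Separately, an AE caused by a rescue drug is counted under the spray given in that period. Vital signs, the other safety endpoint, have a fixed schedule to 120 minutes (Section 9.3), but AEs have no fixed comparison window.

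Safety and tolerability is the secondary objective and placebo is the only reference. A difference in the AE table could partly reflect length of stay or rescue use, or a real difference could be blurred by them.

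**Working it through.** The documents give no AE rate, response rate, length of stay or rescue rate, so there is no planned figure to reproduce.

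**Step 1: where the window ends.**

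| Place | End of AE collection |
|---|---|
| Synopsis, Safety Analysis | Discharge |
| Section 13.1 | Discharge |
| Appendix A, AE footnote | Discharge, plus the follow-up call |
| Section 9.1 | While the subject is in the study |

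Appendix A also marks AE assessment at pre-dose in Periods 2 and 3. These statements do not give one window. Under any of them, time under direct observation still varies with discharge.

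**Step 2: size of an artefact from unequal time.** All inputs are assumptions:
- the same constant AE hazard under both sprays, with incidence *p* over 2 hours;
- a short stay of 2 h and a long stay of *L* h;
- response rates *a* on ARS-1 and *b* on placebo;
- no AEs captured after discharge.

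Incidence over *t* hours is I(t) = 1 − (1 − p)^(t/2). If responders leave early, the gap (placebo minus ARS-1) is (a − b) × [I(L) − I(2)].

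Central case, p = 0.20, L = 4, a = 0.7, b = 0.3:
- I(2) = 0.20 and I(4) = 1 − 0.8² = 0.36.
- Mean stay: ARS-1 0.7×2 + 0.3×4 = 2.6 h; placebo 0.3×2 + 0.7×4 = 3.4 h.
- Incidence: ARS-1 0.7×0.20 + 0.3×0.36 = 24.8%; placebo 0.3×0.20 + 0.7×0.36 = 31.2%.
- Gap: 6.4 points, or 0.064 × 32 ≈ 2 subjects, with no true difference.

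If responders stay longer (chronic spontaneous urticaria, baseline read as pre-dose), the figures swap: ARS-1 31.2%, placebo 24.8%. On that reading an even mix of the two disease types would cancel: 0.5×24.8 + 0.5×31.2 = 28.0% on both sprays.

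Range, with p from 0.10 to 0.30, L from 3 to 5 h, and response 60/40 or 70/30:
- Smallest: 0.2 × [(1 − 0.9^1.5) − 0.10] = 0.2 × 0.046 = 0.9 points.
- Largest: 0.4 × [(1 − 0.7^2.5) − 0.30] = 0.4 × 0.290 = 11.6 points.
- Largest with L held at 4 h: 0.4 × (0.51 − 0.30) = 8.4 points.

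If every AE arises in the first 2 hours, or everyone leaves at 2 hours, the gap is 0.

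**Step 3: AEs from rescue.** Assume a 10% AE risk without rescue, a share *r* rescued and an AE risk *q* from the rescue drug. Incidence is 1 − 0.9 × (1 − r×q).
- Placebo, r = 0.3, q = 0.1: 12.7%. The excess over 10% is 0.027/0.127 = 21% of placebo subjects with an AE.
- Placebo, r = 0.5, q = 0.2: 19.0%. The corresponding share is 0.09/0.19 = 47%.
- ARS-1, r = 0.1, with the same two values of q: 10.9% and 11.8%. Its column is affected too.

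**Step 4: effect of a common window.** With onset limited to 0-120 minutes for everyone, incidence is I(2) on both sprays under equal hazard (20% each in the central case), whatever the response rate. The artefact from unequal time is then 0. AEs from rescue given before 120 minutes remain in the table, so they need a flag.

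**The case against.** The case against has real force, and several stronger readings fail.

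- A reader might infer that AE ascertainment stops at discharge. Appendix A adds the follow-up call and Section 9.1 the time in study, so it need not. If AEs from the call are counted, the windows are less unequal than Step 2 assumes. This does not make them equal, because telephone recall is not the same ascertainment as questioning in the clinic.
- A reader might infer that the windows must differ. The 2-hour minimum covers early AEs equally, and a constant hazard after a single dose is what produces the gap. Unequal time is possible, not certain.
- A reader might infer that the placebo column is inflated in acute flares and the ARS-1 column in chronic spontaneous urticaria. Neither is established. Section 14.3.1 defines baseline as pre-dose for the primary endpoints, but the discharge rules do not say which baseline they mean. If it is the usual non-flare state, the reversal does not follow.
- A reader might attribute late placebo AEs to rescue drugs. Rescue can also follow ARS-1, rescue use is recorded, and the causality categories in Section 13.1 allow for other drugs. That is case-by-case judgement, however, and it does not change the incidence counts.
- A 5-hour stay fits poorly with Sections 3.3 and 6.0, which let a return to baseline beyond 4 hours in chronic spontaneous urticaria be patient-recorded and reported by call.

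Safety is descriptive and the Synopsis calls all analyses exploratory, so no test or power figure is affected. Section 14.5 and parts of Sections 10.3 and 10.4 and Appendix A are redacted; nothing is inferred from them.

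**Conclusion.** The point holds in a limited form. As the visible text stands, the AE table can compare treatments over unequal, response-dependent in-clinic time and counts post-rescue AEs under the spray. The stated end of the AE window is inconsistent across the Synopsis, Sections 9.1 and 13.1, and Appendix A.

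The direction is uncertain. The size is zero if AEs arise within 2 hours and about 1 to 12 points under the assumed grid. The central 6 points, about 2 of 32 subjects, supposes that all subjects follow one discharge pattern and that nothing is captured after discharge. None of these inputs comes from the documents, so the figures show what is possible and do not estimate a bias. The documents do not support saying that either column is inflated or that an ARS-1 effect is masked.

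This is a cheap improvement to a descriptive analysis.

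**What to change.** In Section 14.4:

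1. Add a by-treatment table of AEs with onset 0-120 minutes after dosing for all subjects in the safety set. The 2-hour minimum stay supports it.
2. Do not censor this table at rescue. Rescue can be given before 120 minutes, so ending follow-up there would again shorten observation for non-responders. Flag AEs with onset after rescue and show the table with and without them, reading the second version as a sensitivity display.
3. Tabulate AEs after 120 minutes separately, with time since dose, rescue given, and time under in-clinic observation by treatment.
4. Keep the all-AE table as planned.

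Reconcile the AE window in the Synopsis, Sections 9.1 and 13.1, and the Appendix A footnote, and state whether AEs from the follow-up call enter the by-treatment tables.

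The cost is wording and one extra fixed-window table, with the later AEs shown apart from it. AE onset times and rescue use are already collected; confirm that the clock time of rescue is captured. No visit, procedure or clinical rule changes. The downside is that later AEs sit outside the fixed-window comparison.
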